### **5.3.2 Eliciting Adverse Event Information**

A consistent methodology of non-directive questioning should be adopted for eliciting adverse event information at all patient evaluation timepoints. Examples of non-directive questions include the following:

"How have you felt since your last clinic visit?"

"Have you had any new or changed health problems since you were last here?"

### **5.3.3 Assessment of Severity of Adverse Events**

The adverse event severity grading scale for the National Cancer Institute Common Terminology for Adverse Events, Version 4.0 (NCI CTCAE v4.0) will be used for assessing adverse event severity. [Table 4](#) will be used for assessing severity for adverse events that are not specifically listed in the NCI CTCAE.

**Table 4 Adverse Event Severity Grading Scale for Events Not Specifically Listed in NCI CTCAE**

Grade	Severity
1	Mild; asymptomatic or mild symptoms; clinical or diagnostic observations only; or intervention not indicated
2	Moderate; minimal, local, or non-invasive intervention indicated; or limiting age-appropriate instrumental activities of daily living a
3	Severe or medically significant, but not immediately life-threatening; hospitalization or prolongation of hospitalization indicated; disabling; or limiting self-care activities of daily living b,c
4	Life-threatening consequences or urgent intervention indicated d
5	Death related to adverse event d

NCI CTCAE = National Cancer Institute Common Terminology Criteria for Adverse Events.

Note: Based on the most recent version of NCI CTCAE (v4.0), which can be found at: [http://ctep.cancer.gov/protocolDevelopment/electronic\\_applications/ctc.htm](http://ctep.cancer.gov/protocolDevelopment/electronic_applications/ctc.htm)

a Instrumental activities of daily living refer to preparing meals, shopping for groceries or clothes, using the telephone, managing money, etc.

b Examples of self-care activities of daily living include bathing, dressing and undressing, feeding oneself, using the toilet, and taking medications, as performed by patients who are not bedridden.

c If an event is assessed as a "significant medical event," it must be reported as a serious adverse event (see Section [5.4.2](#) for reporting instructions), per the definition of serious adverse event in Section [5.2.2](#).

d Grade 4 and 5 events must be reported as serious adverse events (see Section [5.4.2](#) for reporting instructions), per the definition of serious adverse event in Section [5.2.2](#).

### **5.3.4 Assessment of Causality of Adverse Events**

Investigators should use their knowledge of the patient, the circumstances surrounding the event, and an evaluation of any potential alternative causes to determine whether an adverse event is considered to be related to the study drug, indicating "yes" or "no"

accordingly. The following guidance should be taken into consideration (see also [Table 5](#)):

- Temporal relationship of event onset to the initiation of study drug
- Course of the event, considering especially the effects of dose reduction, discontinuation of study drug, or reintroduction of study drug (as applicable)
- Known association of the event with the study drug or with similar treatments
- Known association of the event with the disease under study
- Presence of risk factors in the patient or use of concomitant medications known to increase the occurrence of the event
- Presence of non-treatment-related factors that are known to be associated with the occurrence of the event

**Table 5 Causal Attribution Guidance**

Is the adverse event suspected to be caused by the study drug on the basis of facts, evidence, science-based rationales, and clinical judgment?	
YES	There is a plausible temporal relationship between the onset of the adverse event and administration of the study drug, and the adverse event cannot be readily explained by the patient's clinical state, intercurrent illness, or concomitant therapies; and/or the adverse event follows a known pattern of response to the study drug; and/or the adverse event abates or resolves upon discontinuation of the study drug or dose reduction and, if applicable, reappears upon re-challenge.
NO	An adverse event will be considered related, unless it fulfills the criteria specified below. Evidence exists that the adverse event has an etiology other than the study drug (e.g., preexisting medical condition, underlying disease, intercurrent illness, or concomitant medication); and/or the adverse event has no plausible temporal relationship to administration of the study drug (e.g., cancer diagnosed 2 days after first dose of study drug).

### **5.3.5 Procedures for Recording Adverse Events**

Investigators should use correct medical terminology/concepts when recording adverse events on the Adverse Event eCRF. Avoid colloquialisms and abbreviations. Use NCI CTCAE (v4.0) terminology each time it is possible.

Only one adverse event term should be recorded in the event field on the Adverse Event eCRF.

#### **5.3.5.1 Infusion-Related Reactions and Cytokine-Release Syndrome**

There may be significant overlap in signs and symptoms of IRRs and cytokine-release syndrome (CRS). While IRRs occur during or within 24 hours after treatment administration, time to onset of CRS may vary. Differential diagnosis should be applied, particularly for late-onset CRS (occurring more than 24 hours after treatment administration), to rule out other etiologies such as delayed hypersensitivity reactions,

sepsis or infections, HLH, tumor lysis syndrome, early disease progression, or other manifestations of systemic inflammation.

Adverse events that occur during or within 24 hours after study treatment administration and are judged to be related to study treatment infusion should be captured on the Adverse Event eCRF as a diagnosis (e.g., "infusion-related reaction" or "cytokine-release syndrome"). Avoid ambiguous terms such as "systemic reaction." Cases of late-onset CRS should be reported as "cytokine-release syndrome" on the Adverse Event eCRF. Associated signs and symptoms of an IRR should be recorded on the dedicated Infusion-Related Reaction eCRF.

If a patient experiences both a local and systemic reaction to a single administration of study treatment, each reaction should be recorded separately on the Adverse Event eCRF, with associated signs and symptoms of an IRR also recorded separately on the dedicated Infusion-Related Reaction eCRF.

In recognition of the challenges in clinically distinguishing between IRRs and CRS, consolidated guidelines for medical management of IRRs and CRS are provided in [Appendix 11](#).

#### **5.3.5.2 Diagnosis versus Signs and Symptoms**

For adverse events, a diagnosis (if known) should be recorded on the Adverse Event eCRF rather than individual signs and symptoms (e.g., record only liver failure or hepatitis rather than jaundice, asterixis, and elevated transaminases). However, if a constellation of signs and/or symptoms cannot be medically characterized as a single diagnosis or syndrome at the time of reporting, each individual event should be recorded on the Adverse Event eCRF. If a diagnosis is subsequently established, all previously reported adverse events based on signs and symptoms should be nullified and replaced by one adverse event report based on the single diagnosis, with a starting date that corresponds to the starting date of the first symptom of the eventual diagnosis.

#### **5.3.5.3 Adverse Events That Are Secondary to Other Events**

In general, adverse events that are secondary to other events (e.g., cascade events or clinical sequelae) should be identified by their primary cause, with the exception of severe or serious secondary events. A medically significant secondary adverse event that is separated in time from the initiating event should be recorded as an independent event on the Adverse Event eCRF. For example:

- If vomiting results in mild dehydration with no additional treatment in a healthy adult, only vomiting should be reported on the eCRF.
- If vomiting results in severe dehydration, both events should be reported separately on the eCRF.
- If a severe gastrointestinal hemorrhage leads to renal failure, both events should be reported separately on the eCRF.

- If dizziness leads to a fall and consequent fracture, all three events should be reported separately on the eCRF.
- If neutropenia is accompanied by an infection, both events should be reported separately on the eCRF.

All adverse events should be recorded separately on the Adverse Event eCRF if it is unclear as to whether the events are associated.

#### **5.3.5.4 Persistent or Recurrent Adverse Events**

A persistent adverse event is one that extends continuously, without resolution, between patient evaluation timepoints. Such events should only be recorded once on the Adverse Event eCRF. The initial severity (intensity or grade) of the event will be recorded at the time the event is first reported. If a persistent adverse event becomes more severe, the most extreme severity should also be recorded on the Adverse Event eCRF. If the event becomes serious, it should be reported to the Sponsor immediately (i.e., no more than 24 hours after learning that the event became serious; see Section 5.4.2 for reporting instructions). The Adverse Event eCRF should be updated by changing the event from "non-serious" to "serious," providing the date that the event became serious, and completing all data fields related to serious adverse events.

A recurrent adverse event is one that resolves between patient evaluation timepoints and subsequently recurs. Each recurrence of an adverse event should not be recorded as a separate event on the Adverse Event eCRF, but the "intermittent" box should be ticked.

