### **2.1 PRIMARY OBJECTIVE**

The primary objective of this study is to evaluate the safety of atezolizumab based on the following endpoints:

- Nature, severity, duration, frequency and timing of adverse events (AEs)
- Changes in vital signs, physical findings, and clinical laboratory results during and following atezolizumab administration

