## **6.4 PRIMARY SAFETY ANALYSIS**

The primary endpoint of the study is the incidence of treatment-emergent AEs. Verbatim descriptions of AEs will be mapped to MedDRA thesaurus terms and graded according to the National Cancer Institute Common Terminology Criteria version 4.0. Multiple occurrences of the same event will be counted once at the maximum severity.

Other safety variables will include:

- Drug exposure (e.g., treatment duration, number of doses, dose intensity and dose modifications/discontinuations, with reasons)
- All AEs
- SAEs
- AEs (grade 3–5)
- AEs of special interest
- AEs leading to study drug discontinuation or interruption
- Changes in vital signs from baseline
- Changes in physical findings from baseline
- Changes in selected laboratory parameters from baseline
- Deaths and cause of death
- Concomitant medications

The incidence of AEs will be summarized by frequency tables. Corresponding 95% Clopper-Pearson confidence intervals (CIs) will be presented, as applicable. Time to first incidence of selected event types will also be estimated and presented graphically using the Kaplan-Meier method.

Treatment exposure, discontinuation rate, and cause of death will be analyzed by frequency tables. When appropriate, median time on treatment and 95% CI will be estimated by the Kaplan-Meier approach or using univariate statistics, presenting mean, median, quartiles, minimum, maximum and standard deviation.

Changes in vital signs and physical findings from baseline will be tabulated and presented graphically when applicable.

Worst grades for laboratory parameters and newly occurring Grade 3 and 4 laboratory values during treatment will be summarized by frequency tables.

Concomitant medications recorded during the study will be summarized by frequency tables.

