2.2.5 Safety Outcome Measures

The following endpoints are defined to evaluate safety:

- Nature, severity, duration, frequency and timing of AEs.
- Changes in vital signs, physical findings, and clinical laboratory results during and following atezolizumab administration.

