AEs with onset on first dosing date, not recorded as starting before study treatment administration will be considered as TEAEs. Similarly, AEs with onset date prior first dosing date but worsening/change recorded on or after first dosing date will be considered as TEAEs.

Only TEAEs will be included in summary tables. AEs which are not treatment-emergent will only be included in the AE listings.

Patient rates for AEs will be presented and accompanied by the respective two-sided 95% Pearson-Clopper CIs.

In any AE summary tables, number and percentage of patients reporting at least one AE will be provided. In AE summary tables by SOC and PT, the number of reported events will be presented additionally.

Every occurrence of an AE in any patient will be counted in the total number of events.

In tables presenting frequency of AEs by worst grade, only the event with the highest grade will be counted when there are multiple occurrences of a same AE in one patient.

A missing NCI CTCAE grade will be imputed as follows: for a fatal AE, as Grade 5; for a non-fatal AE, as Grade 4.

A summary table will be provided presenting:

- Number and percentage of patients with any TEAE
- Number and percentage of patients with any Serious TEAE
- Number and percentage of patients with any related TEAE
- Number and percentage of patients with any related Serious TEAE
- Number and percentage of patients with any TEAE leading to study drug discontinuation
- Number and percentage of patients with any grade 3 to 4 TEAE
- Number and percentage of patients with any grade 5 TEAE
- Number and percentage of patients with any AESI
- Number and percentage of patients with any grade 3 to 5 AESI
- Number and percentage of deaths, overall and by reason
- Number and percentage of deaths on study treatment (i.e. within 30 days post last study treatment administration), overall and by reason

Following safety data will be summarized:

- TEAEs by SOC, PT and by worst grade
- TEAEs of grade 3 to 5, by PT and by worst grade
- TEAEs of grade 5, by PT
- TEAEs leading to study drug discontinuation, by SOC and PT
- TEAEs leading to study discontinuation, by SOC and PT
- TEAEs related to study drug, by SOC, PT and worst grade
- Serious TEAEs by SOC, PT and worst grade
- Serious TEAEs related to study drug, by SOC and PT
- AEs of special interest by category, PT and worst grade (with additional column for AESI of grade ≥ 3)

Death cases will be summarized as follows:

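### SAP 4.6.2 has no adverse-event onset or duration output, although both fall under the primary objective and the protocol promises the onset analysis; its count of every occurrence cannot be met from the eCRF

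*Protocol*

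**What the plan says.** **Objective.** SAP 2.2.5 lists as a safety outcome "Nature, severity, duration, frequency and timing of AEs". Protocol 2.1 has the same five attributes under the primary objective.

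**Promised analysis.** Protocol 6.4 states: "Time to first incidence of selected event types will also be estimated and presented graphically using the Kaplan-Meier method". The Protocol synopsis and the synopsis copied into SAP Appendix 1 repeat this. None of the three names the event types.

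**Outputs.** SAP 4.6.2 specifies an overview table, a set of AE summaries, death tables and by-patient listings. Deaths are classified by days since first and last dose. Nothing similar is given for AEs.

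**Recording.** On recurrent AEs, Protocol 5.3.5.4 says "Each recurrence of an adverse event should not be recorded as a separate event on the Adverse Event eCRF"; the site ticks an intermittent box instead. For persistent AEs, also recorded once, the same section adds: "If a persistent adverse event becomes more severe, the most extreme severity should also be recorded on the Adverse Event eCRF". It has no such sentence for recurrent AEs.

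**Counting.** SAP 4.6.2 says "In AE summary tables by SOC and PT, the number of reported events will be presented additionally" and, shortly after, "Every occurrence of an AE in any patient will be counted in the total number of events". In its worst-grade tables "only the event with the highest grade will be counted when there are multiple occurrences of a same AE in one patient".

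**The concern.** The trial exists to describe safety. If SAP 4.6.2 is followed as written, the report will show how many patients had each AE and how severe it was, but not when AEs began or how long they lasted. For immune-mediated events, those are two of the things a safety study of this kind is expected to describe. The protocol's commitment to the onset analysis would lapse without anyone having decided to drop it. If it were added late, the event types and the censoring rule would be chosen with the data in view.

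The counting issue is smaller. A reader of the SOC/PT tables would take the event column as episodes, although the eCRF rule allows only one record for an AE that comes and goes.

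**Working it through.** **1. Tally of SAP 4.6.2.**

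| Output set | Number | With AE onset or duration |
|---|---|---|
| Overview table lines | 11 | 0 |
| AE summaries | 9 | 0 |

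Of the 9 summaries, 6 are by SOC and PT and so carry the event count: all TEAEs, those leading to drug discontinuation, those leading to study discontinuation, related, serious, and serious related. Five use worst grade (all, Grade 3 to 5, related, serious, AESI). Taking out serious TEAEs and AESIs leaves 5 − 2 = 3 that can contain events that are neither serious nor of special interest.

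**2. Tracing the two attributes.**

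| Attribute | Objective | Analysis specified | In SAP 4.6.2 |
|---|---|---|---|
| Timing | Protocol 2.1, SAP 2.2.5 | Protocol 6.4 and synopsis; SAP Appendix 1 | No |
| Duration | Protocol 2.1, SAP 2.2.5 | Nowhere | No |

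Reading timing as time to onset is an interpretation, but Protocol 6.4 supports it. SAP section 4 gives Kaplan-Meier as the general time-to-event method; it names no AE endpoint, event type or censoring rule.

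**3. Why a censoring rule is needed.** SAP 4.6.2 ends the treatment-emergent window 30 days after the last dose, or 90 days for SAEs and AESIs. Protocol 5.1 also stops collection at new anti-cancer therapy, if earlier. A patient who starts new therapy inside the window would still count as at risk although events are no longer collected. Death without the event is a further issue: Protocol 3.3.6 puts median survival in the second-line setting at about 7 to 9 months, so such deaths will be common. If they are censored, one minus Kaplan-Meier overstates the proportion who experience the event.

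**4. Recording against counting.** One record per recurrent AE cannot yield a count of every occurrence. The column headed as reported events therefore counts records. If a share r of records recur with m further episodes each, 1000 records stand for 1000 × (1 + r × m) episodes. The documents give neither r nor m, so no shortfall can be stated.

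**5. What merging does to duration.** Assume, since neither document says, that an intermittent record runs from first onset to last resolution. Two 7-day episodes separated by 14, 42 or 84 days then give spans of 7 + 14 + 7 = 28, 7 + 42 + 7 = 56 and 7 + 84 + 7 = 98 days, against 14 days with the event. Intermittent records should not be pooled with the rest.

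**6. What is not affected.** The plan's precision example is 5 patients in 1000. Lower limit = Beta(0.025; 5, 996) = 0.163%; upper limit = Beta(0.975; 6, 995) = 1.163%; half-width = (1.163 − 0.163)/2 = 0.500%. This matches the printed 0.16%, 1.16% and ±0.5%, and the other eight rows of Protocol Table 6 also reproduce. A patient with one episode or several adds 1 to the numerator either way. Merging recurrences leaves time to first onset of any grade unchanged too.

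**The case against.** **The onset analysis is already planned.** It stands in Protocol 6.4, and SAP 2.1 refers to the appendix that repeats it. This is correct, and it limits the point. A reader might infer that two of the five attributes in the objective have no specified analysis. The documents do not support that: timing has one, which the SAP body does not carry through, and only duration has none.

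**The SAP is for the iDMC.** SAP section 1 says so. But SAP 2.4 sets the timing of the primary and final analyses, SAP 4.4 contains the full efficacy analysis, and SAP 4.8 describes the iDMC reviews as past.

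**The omission may be deliberate, or listings may suffice.** Where the SAP leaves something out it says so: questionnaires at the primary analysis, utility modelling, biomarkers. It is silent here. A by-patient listing is not the estimate that was promised.

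**Reported events already means records.** Largely so. This reduces the conflict to a labelling error. The phrase about every occurrence still has to go.

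**Worst grade.** A reader might infer that severity is understated for recurrent AEs. That is possible, but not shown. The eCRF manual mentioned in Protocol 7.2 was not supplied and may settle it. SAP 4.6.2 refers to recorded worsening, SAEs and AESIs are reported within 24 hours, and worst laboratory grades are tabulated separately in SAP 4.6.3.

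**Competing risks go beyond the promise.** They do. The protocol names only Kaplan-Meier, and the extra estimate is a recommendation.

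**Conclusion.** The main point stands. SAP 4.6.2 does not implement the time-to-first-incidence analysis to which Protocol 6.4 commits, its event types are named nowhere, and no AE duration summary is specified in either document although duration is part of the primary objective. The extent is 0 of 20 listed outputs (11 + 9). This should be corrected before reporting.

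The event count is a minor point: a wrong description of a column in 6 tables. Any loss of grade on intermittent records is unquantified and probably confined to events that are neither serious nor of special interest.

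It would be wrong to conclude that the primary endpoint is biased. Patient-level incidence and its exact intervals do not depend on how recurrences are recorded. Nor are uncertain onset dates for Grade 3 or higher peculiar to intermittent AEs: a persistent AE is also a single record, so its onset too may belong to a lower grade.

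The conclusion rests on reading timing as time to onset, and on the supplied documents without the eCRF manual.

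**What to change.** In SAP 4.6.2:

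1. Add time to first onset for named event types, for example AESIs and Grade 3 or higher TEAEs. Show the promised Kaplan-Meier curve and, beside it, cumulative incidence with death without the event as competing event.
2. State the censoring rule: end of the TEAE window (30 days, or 90 days for SAEs and AESIs) or new anti-cancer therapy, whichever comes first. Grade 3 or higher TEAEs mix both windows, so say which one applies.
3. For Grade 3 or higher onset, flag every single-record AE whose grade changed, persistent as well as intermittent.
4. Add an AE duration summary, with intermittent records shown separately and a rule for unresolved events. If duration or onset is left out on purpose, say so and why.
5. Replace the sentence on counting every occurrence with: number of AE records, intermittent AEs counted once. Add a limitation sentence to the report.
6. Check how existing intermittent records were graded and dated. Have any still to be collected carry the worst grade across recurrences.

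The cost is a few outputs on existing data, one relabelled column and a short site instruction. No extra patients, visits or re-collection of episodes are needed. SAP 3.0 is dated 14 December 2022 and was signed in May 2023, so the site instruction can help only data not yet collected.
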